#### Table 7: Algorithm for Prior/Concomitant medications

| MEDICATION START DATE | MEDICATION STOP DATE | RULE for prior or concomitant categorization   |
|-----------------------|----------------------|--|
| Known                 | Known                | If medication stop date < date of first dose of IMP, assign as prior   |
|                       |                      | If medication stop date >= date of first dose of IMP, assign as concomitant  |
|                       | Partial              | Impute medication stop date as latest possible date (i.e. last day of month if day unknown or 31 st December if day and month are unknown), then: |
|                       |                      | If medication stop date < date of first dose of IMP, assign as prior   |
|                       |                      | If medication stop date >= date of first dose of IMP, assign as concomitant  |
|                       | Missing              | Assign as concomitant  |
|                       |                      |  |
| Partial or Missing    | Known                | If medication stop date < date of first dose of IMP, assign as prior   |
|                       |                      | If medication stop date >= date of first dose of IMP, assign as concomitant  |
|                       | Partial              | Impute medication stop date as latest possible date (i.e. last day of month if day unknown or 31 st December if day and month are unknown), then: |
|                       |                      | If medication stop date < date of first dose of IMP, assign as prior   |
|                       |                      | If medication stop date >= date of first dose of IMP, assign as concomitant  |
|                       | Missing              | Assign as concomitant  |

# 13. Tables, Figures and Listings

# **13.1 Table Conventions**

- If the categories of a parameter are ordered, then all categories between the maximum and minimum category are presented in the table even in case of frequency equal to 0.
- If the categories are not ordered (e.g., Medical History), then only those categories for which there is at least 1 subject represented in 1 or more groups are included.
- Unless otherwise specified, the estimated mean and median for a set of values are printed out to 1 more significant digit than the original values, and standard deviations.
- Missing descriptive statistics or p-values which cannot be estimated are reported as "-".

# **13.2 Listing Conventions**

- Listings will be sorted for presentation in order of subject number, treatment groups (planned), and visit.
- All listings will contain the planned and actual treatment.
- Dates are printed in SAS DATE9.format ("ddMMMyyyy": 01JUL2000). Missing portions of dates are represented on subject listings as dashes (--JUL2000).

# 15. Appendices

# 15.1 Tables

| Number - Title - Population   | KFR | Final analysis |
|---|-----|----------------|
| Table 14.1.1 Subject enrolment and disposition. Screened set  | х   | x              |
| Table 14.1.2.1 Major protocol deviations. Randomized set  |     | x              |
| Table 14.1.2.2 Minor protocol deviations. Randomized set  |     | x              |
| Table 14.1.3.1 Study discontinuation and primary reasons for withdrawal. Randomized set   |     | x              |
| Table 14.1.4.1 Summary of demographic characteristics. Full analysis set  | х   | x              |
| Table 14.1.4.2 Summary of baseline characteristics. Full analysis set   | х   | x              |
| Table 14.1.5.1 Medical History. Full analysis set   |     | x              |
| Table 14.1.5.2 Concomitant diseases. Full analysis set  |     | x              |
| Table 14.1.6.1 Prior medication. Full analysis set  |     | x              |
| Table 14.1.6.2 Concomitant medication. Full analysis set  |     | x              |
| Table 14.1.6.3 Prior medication. Safety analysis set  |     | x              |
| Table 14.1.6.4 Concomitant medication. Safety analysis set  |     | x              |
| Table 14.1.7 Dry Eye History. Full analysis set   |     | x              |
| Table 14.1.8.1 Other baseline characteristics: Eligible eye, SANDE scores, IDEEL scores, Schirmer test I and Schirmer test II. Full analysis set                          |     | x              |
| Table 14.1.8.2 Other baseline characteristics by eye: BCDVA, External ocular examination, Slit Lamp Ophthalmic Exam, NEI scale and TFBUT.
Full analysis set            |     | x              |
| Table 14.2.1.1 Schirmer I test (without anesthesia) >10mm/5min at week 4 - Logistic regression model - Multiple imputation. Full analysis set                             | x   | x              |
| Table 14.2.1.2 Change from baseline in the global SANDE score at week 12 - Analysis of Covariance (ANCOVA) - Multiple imputation. Full analysis set                       | x   | x              |
| Table 14.2.2.1 Sensitivity analysis: Schirmer I test (without anesthesia) >10mm/5min at week 4 - Logistic regression model - Multiple imputation. Full analysis set       |     | x              |
| Table 14.2.2.2 Sensitivity analysis: Change from baseline in the global SANDE score at week 12 - Analysis of Covariance (ANCOVA) - Multiple imputation. Full analysis set |     | x              |

| Number - Title - Population  | KFR | Final analysis |
|--|-----|----------------|
| Table 14.2.2.3 Sensitivity analysis: Schirmer I test (without anesthesia) >10mm/5min at week 4 - Logistic regression model – Tipping point. Full |     | v              |
| analysis set   |     | X              |
| Table 14.2.2.4 Sensitivity analysis: Change from baseline in the global SANDE score at week 12 - Analysis of Covariance (ANCOVA) - Tipping       |     | v              |
| point. Full analysis set   |     | ^              |
| Table 14.2.3.1 Supportive analysis: Schirmer I test (without anesthesia) >10mm/5min at week 4 - Logistic regression model – Complete cases       |     | ×              |
| only. Full analysis set  |     | ^              |
| Table 14.2.3.2 Supportive analysis: Change from baseline in the global SANDE score at week 12 - Analysis of Covariance (ANCOVA) - Complete       |     | x              |
| cases only. Full analysis set  |     | ^              |
| Table 14.2.3.3 Supportive analysis: Schirmer I test (without anesthesia) >10mm/5min at week 4 - Logistic regression model – Multiple             |     | x              |
| imputation. Per Protocol analysis set  |     | ^              |
| Table 14.2.3.4 Supportive analysis: Change from baseline in the global SANDE score at week 12 - Analysis of Covariance (ANCOVA) - Multiple       |     | x              |
| imputation. Per Protocol analysis set  |     | ^              |
| Table 14.2.4.1 Schirmer I test (without anesthesia) >10mm/5min at week 8 - Logistic regression model - Multiple imputation. Full analysis set    |     | х              |
| Table 14.2.4.2 Change from baseline in the severity SANDE score at week 12 - Analysis of Covariance (ANCOVA) - Multiple imputation. Full         |     | v              |
| analysis set   |     | X              |
| Table 14.2.4.3 Change from baseline in the frequency SANDE score at week 12 - Analysis of Covariance (ANCOVA) - Multiple imputation. Full        |     | ×              |
| analysis set   |     | ^              |
| Table 14.2.4.4.1.1 Change from baseline in the IDEEL Quality of Life module (Daily activities) up to week 12 - MMRM - Multiple imputation.       |     | ~              |
| Full analysis set  |     | ^              |
| Table 14.2.4.4.1.2 Change from baseline in the IDEEL Quality of Life module (Feelings) up to week 12 - MMRM - Multiple imputation. Full          |     | ×              |
| analysis set   |     | ^              |
| Table 14.2.4.4.1.3 Change from baseline in the IDEEL Quality of Life module (Work) up to week 12 - MMRM - Multiple imputation. Full analysis     |     | ×              |
| set  |     | ^              |
| Table 14.2.4.4.2.1 Change from baseline in the IDEEL Dry eye Treatment satisfaction & Bother module (Treatment – In General) up to week 12       |     | ×              |
| - MMRM - Multiple imputation. Full analysis set  |     | ^              |
| Table 14.2.4.4.2.2 Change from baseline in the IDEEL Dry eye Treatment satisfaction & Bother module (Treatment – Eye drops) up to week 12 -      |     | x              |
| MMRM - Multiple imputation. Full analysis set  |     | ^              |
| Table 14.2.4.4.3 Change from baseline in the IDEEL Dry eye Symptom bother module up to week 12 - MMRM - Multiple imputation. Full                |     | x              |
| analysis set   |     | ~              |
| Table 14.2.4.5 Change from baseline in the Cornea and conjunctiva vital staining with fluorescein NEI scale up to week 12 - MMRM - Multiple      |     | x              |
| imputation. Full analysis set  |     |                |
| Table 14.2.4.6 Change from baseline in the TFBUT up to week 12 - MMRM - Multiple imputation. Full analysis set                                   |     | x              |

| Number - Title - Population   | KFR | Final analysis |
|---|-----|----------------|
| Table 14.2.5.1 Absolute values and change from baseline in Schirmer I test at each timepoint. Full analysis set   | х   | x              |
| Table 14.2.5.2.1 Absolute values and change from baseline in SANDE global scores at each timepoint. Full analysis set   | х   | x              |
| Table 14.2.5.2.2 Absolute values and change from baseline in SANDE severity scores at each timepoint. Full analysis set   | х   | x              |
| Table 14.2.5.2.3 Absolute values and change from baseline in SANDE frequency scores at each timepoint. Full analysis set  | х   | x              |
| Table 14.2.5.3 Number of patients experienced a worsening in symptom scores (SANDE global score) and/or NEI score ≥ 50% assessed at week 4. Full analysis set   |     | x              |
| Table 14.2.5.4.1 Absolute values and change from baseline in IDEEL Quality of Life module at each timepoint. Full analysis set  | х   | x              |
| Table 14.2.5.4.2 Absolute values and change from baseline in IDEEL Dry eye Treatment satisfaction & Bother module at each timepoint. Full analysis set  | x   | x              |
| Table 14.2.5.4.3 Absolute values and change from baseline in IDEEL Dry eye Symptom bother module at each timepoint. Full analysis set   | х   | x              |
| Table 14.2.5.5 Absolute values and change from baseline in Cornea and conjunctiva vital staining with fluorescein (NEI scale) at each timepoint. Full analysis set  | x   | x              |
| Table 14.2.5.6 Absolute values and change from baseline in TFBUT at each timepoint. Full analysis set   | х   | x              |
| Table 14.2.6.1.1 Subgroup evaluation: Schirmer I test (without anesthesia) >10mm/5min at week 4 - Treatment by region interaction- Logistic regression model - Multiple imputation. Full analysis set                               |     | x              |
| Table 14.2.6.1.2 Subgroup evaluation: Schirmer I test (without anesthesia) >10mm/5min at week 4 - Treatment by Sjögren's syndrome interaction- Logistic regression model - Multiple imputation. Full analysis set                   |     | x              |
| Table 14.2.6.1.3 Subgroup evaluation: Schirmer I test (without anesthesia) >10mm/5min at week 4 - Treatment by medical history interaction-
Logistic regression model - Multiple imputation. Full analysis set                   |     | x              |
| Table 14.2.6.1.4 Subgroup evaluation: Schirmer I test (without anesthesia) >10mm/5min at week 4 - Treatment by concomitant medication interaction- Logistic regression model - Multiple imputation. Full analysis set               |     | x              |
| Table 14.2.6.2.1 Subgroup evaluation: Change from baseline in the global SANDE score at week 12 - Analysis of Covariance (ANCOVA) -
Treatment by region interaction- Multiple imputation. Full analysis set                      |     | x              |
| Table 14.2.6.2.2 Subgroup evaluation: Change from baseline in the global SANDE score at week 12 - Analysis of Covariance (ANCOVA) - Treatment by Sjögren's syndrome interaction- Multiple imputation. Full analysis set             |     | x              |
| Table 14.2.6.2.3 Subgroup evaluation: Change from baseline in the global SANDE score at week 12 - Analysis of Covariance (ANCOVA) -
Treatment by medical history interaction- Multiple imputation. Full analysis set             |     | x              |
| Table 14.2.6.2.4 Subgroup evaluation: Change from baseline in the global SANDE score at week 12 - Analysis of Covariance (ANCOVA) -         Treatment by concomitant medication interaction- Multiple imputation. Full analysis set |     | x              |
| Table 14.2.6.3.1 Absolute values and change from baseline in Schirmer I test at each timepoint by age class. Full analysis set  |     | x              |

| Number - Title - Population   | KFR | Final analysis |
|---|-----|----------------|
| Table 14.2.6.4.1 Absolute values and change from baseline in Cornea and conjunctiva vital staining with fluorescein (NEI scale) at each                               |     | x              |
| timepoint by age class. Full analysis set   |     | ^              |
| Table 14.2.6.5.1 Absolute values and change from baseline in TFBUT at each timepoint by age class. Full analysis set  |     | x              |
| Table 14.2.6.6.1.1 Absolute values and change from baseline in SANDE global scores at each timepoint by age class. Full analysis set                                  |     | x              |
| Table 14.2.6.6.2.1 Absolute values and change from baseline in SANDE severity scores at each timepoint by age class. Full analysis set                                |     | x              |
| Table 14.2.6.6.3.1 Absolute values and change from baseline in SANDE frequency scores at each timepoint by age class. Full analysis set                               |     | x              |
| Table 14.2.6.7.1.1 Absolute values and change from baseline in IDEEL Quality of Life module at each timepoint by age class. Full analysis set                         |     | x              |
| Table 14.2.6.7.2.1 Absolute values and change from baseline in IDEEL Dry eye Treatment satisfaction & Bother module at each timepoint by age class. Full analysis set |     | x              |
| Table 14.2.6.7.3.1 Absolute values and change from baseline in IDEEL Dry eye Symptom bother module at each timepoint by age class. Full analysis set                  |     | x              |
| Table 14.2.6.y.x Repeated set of tables form 14.2.6.3.1 to 14.2.6.2.7.3.1 for all subgroups   |     | x              |
| Table 14.3.1.1 Summary of treatment emergent adverse events (TEAE). Safety set  |     | x              |
| Table 14.3.1.2 Summary of Ophthalmic TEAEs by primary SOC and PT by study periods. Safety set   |     | x              |
| Table 14.3.1.3 Summary of Non-Ophthalmic TEAEs by primary SOC and PT by study periods. Safety set   |     | x              |
| Table 14.3.1.4 Summary of TEAEs by primary SOC and PT by severity. Safety set   |     | x              |
| Table 14.3.1.5 Summary of Serious TEAEs by primary SOC and PT by study periods. Safety set  |     | x              |
| Table 14.3.1.6 Summary of ADRs by primary SOC and PT by study periods. Safety set   |     | x              |
| Table 14.3.1.7 Summary of ADRs by primary SOC and PT by severity. Safety set  |     | x              |
| Table 14.3.1.8 Summary of TEAEs leading to IMP discontinuation by primary SOC and PT by study periods. Safety set   |     | x              |
| Table 14.3.1.9 Summary of TEAEs leading to study discontinuation by primary SOC and PT by study periods. Safety set   |     | x              |
| Table 14.3.1.10 Summary of TEAEs leading to death by primary SOC and PT. Safety set   |     | x              |
| Table 14.3.2.1.1 Compliance to IMP. Full analysis set   |     | x              |
| Table 14.3.2.1.2 Compliance to IMP. Safety set  |     | x              |
| Table 14.3.2.2.1 Extent of exposure. Full analysis set  |     | x              |
| Table 14.3.2.2.2 Extent of exposure. Safety set   |     | x              |
| Table 14.3.2.3.1 Use of preservative free artificial tears. Full analysis set   |     | x              |
| Table 14.3.2.3.2 Use of preservative free artificial tears. Safety set  |     | x              |

# 15.2 Listings

| Number - Title - Population K   | FR | Final analysis |
|---|----|----------------|
| Listing 16.1.7 Randomisation Scheme. Randomized set   |    | x              |
| Listing 16.2.1 Patient disposition in analysis data sets and primary reasons for withdrawal. Enrolled set |    | x              |
| Listing 16.2.2 Protocol deviations. Randomized set  |    | x              |
| Listing 16.2.3.1 Study discontinuation and reasons for withdrawal. Randomized set                         |    | x              |
| Listing 16.2.3.2 Study Visits. Randomized set   |    | x              |
| Listing 16.2.4.1 Demographic data. Safety set   |    | x              |
| Listing 16.2.4.2 Baseline Characteristics. Safety set   |    | x              |
| Listing 16.2.4.3 Medical history. Safety set  |    | x              |
| Listing 16.2.4.4 Concomitant Diseases. Safety set   |    | x              |
| Listing 16.2.4.5 Prior medication and therapy. Safety set   |    | x              |
| Listing 16.2.4.6 Concomitant medication and therapy. Safety set   |    | x              |
| Listing 16.2.4.7 Dry Eye History. Safety set  |    | x              |
| Listing 16.2.5.1 Compliance to IMP. Safety set  |    | x              |
| Listing 16.2.5.2 Exposure to IMP. Safety set  |    | x              |
| Listing 16.2.5.3 Use of preservative free artificial tears. Safety set                                    |    | x              |
| Listing 16.2.6.1 Schirmer test I by patient and visit. Safety set   |    | x              |
| Listing 16.2.6.2 Schirmer test II by patient and visit. Safety set  |    | x              |
| Listing 16.2.6.3 SANDE scores by patient and visit. Safety set  |    | x              |
| Listing 16.2.6.4 NEI scale by patient and visit. Safety set   |    | x              |
| Listing 16.2.6.5 TFBUT by patient and visit. Safety set   |    | x              |
| Listing 16.2.6.6 IDEEL scores by patient and visit. Safety set  |    | x              |
| Listing 16.2.7.1 Listing of all AEs by Patient. Safety set  |    | x              |
| Listing 16.2.7.2 Listing of all AEs leading to IMP discontinuation. Safety set                            |    | x              |
| Listing 16.2.7.3 Listing of all AEs leading to study discontinuation. Safety set                          |    | x              |
| Listing 16.2.7.4 Listing of SAEs by Patient. Safety set   |    | x              |

Page 49 of 54

| Number - Title - Population                            | KFR | Final analysis |
|--|-----|----------------|
| Listing 16.2.7.5 Listing of ADR by Patient. Safety set |     | x              |
| Listing 16.2.7.6 Listing of Deaths. Safety set         |     | x              |

# 15.3 Figures

| Number - Title - Population   | KFR | Final analysis |
|---|-----|----------------|
| Figure 14.1.3.2 Time from randomization to discontinuation (Kaplan-Meier) . Randomized set  |     | x              |
| Figure 14.2.3.5 Tipping point Shirmer test. Full analysis set   |     | x              |
| Figure 14.2.3.6 Tipping point plot SANDE. Full analysis set   |     | x              |
| Figure 14.2.5.1.1 Schirmer I test Observed Mean (±SEM) at each timepoint. Full analysis set   |     | x              |
| Figure 14.2.5.1.2 Schirmer I test Mean change from baseline (±SEM) at each timepoint. Full analysis set                                   |     | x              |
| Figure 14.2.5.1.3 Observed percentage of patients with Schirmer I test >10mm/5min at each timepoint. Full analysis set                    |     | x              |
| Figure 14.2.5.2.1.1 SANDE global score Observed Mean (±SEM) at each timepoint. Full analysis set  |     | x              |
| Figure 14.2.5.2.1.2 SANDE global score Mean change from baseline (±SEM) at each timepoint. Full analysis set                              |     | x              |
| Figure 14.2.5.5.1 Cornea and conjunctiva vital staining total score Observed Mean (±SEM) at each timepoint. Full analysis set             |     | x              |
| Figure 14.2.5.5.2 Cornea and conjunctiva vital staining total score Mean change from baseline (±SEM) at each timepoint. Full analysis set |     | x              |
| Figure 14.2.5.6.1 TFBUT Observed Mean (±SEM) at each timepoint. Full analysis set   |     | x              |
| Figure 14.2.5.6.2 TFBUT Mean change from baseline (±SEM) at each timepoint. Full analysis set   |     | x              |

# **15.4 SAS Code for the primary analysis**

# 15.4.1 Schirmer I test >10mm/5min at week 4

| Standard   | Alternative code in case of no convergence  |
|--|---|
| PROC MI DATA= EFFICACY01 NIMPUTE=200 SEED=180404 OUT=EFFICACY_MONO1;
VAR BASVAL SCHIRMER_W2 AVAL;
MCMC CHAIN=SINGLE NBITER=200 NITER=100
IMPUTE=MONOTONE;
WHERE TRT=1;
RUN;
PROC MI DATA=EFFICACY01 NIMPUTE=200 SEED=180404 OUT=EFFICACY_MONO2;
VAR BASVAL SCHIRMER_W2 AVAL;
MCMC CHAIN=SINGLE NBITER=200 NITER=100
IMPUTE=MONOTONE;
WHERE TRT=2;
RUN;
DATA EFFICACY_MONO;
SET EFFICACY_MONO1 EFFICACY_MONO2;
RUN; | PROC MI DATA= EFFICACY01 NIMPUTE=200 SEED=180404 OUT=EFFICACY_MONO;
VAR BASVAL TRT SCHIRMER_W2 AVAL;
MCMC CHAIN=SINGLE NBITER=200 NITER=100
IMPUTE=MONOTONE;
RUN;   |
| PROC SORT;
BY_IMPUTATION_SUBJID;
RUN;  |   |
| PROC MI DATA=EFFICACY_MONO SEED=200582 NIMPUTE=1 OUT=EFFICACY_IMP;
BY_IMPUTATION_;
CLASS TRT AGE SEX EOTSTT;
MONOTONE REG(AVAL = TRT AGEc SEX BASVAL / DETAILS);
MNAR MODEL(AVAL / MODELOBS= (EOTSTT='NOT COMPLETED'));
VAR TRT AGE SEX BASVAL SCHIRMER_W2 AVAL;
RUN;  | PROC MI DATA=EFFICACY_MONO SEED=200582 NIMPUTE=1 OUT=EFFICACY_IMP;
BY_IMPUTATION_;
CLASS TRT AGE SEX EOTSTT;
MONOTONE REG(AVAL = TRT AGE SEX BASVAL / DETAILS);
MNAR MODEL(AVAL / MODELOBS= (TRT=2 /*Vehicle*/));
VAR TRT AGE SEX BASVAL SCHIRMER_W2 AVAL;
RUN; |

| Standard   | Alternative code in case of no convergence |
|--|--|
| DATA EFFICACY_IMP;
SET EFFICACY_IMP;
IF AVAL>10 THEN AVALC='Y';
ELSE AVALC='N';
RUN;
ODS OUTPUT DIFFS=GLIMMIX_DIFFS;  |  |
| ODS OUTPUT PARAMETERESTIMATES=ESTIMATES;
PROC GLIMMIX DATA=EFFICACY_IMP METHOD = QUAD;
BY_IMPUTATION_;
CLASS TRT(REF="2") AGE(REF="<=Median") SEX(REF="F") SITEID;
MODEL AVALC(EVENT='Y')=TRT AGEc SEX BASVAL /S DIST=BINARY LINK=LOGIT OR;
RANDOM INTERCEPT / SUBJECT=SITEID;
LSMEANS TRT / ILINK ODDSRATIO CL DIFF=control("2");
RUN; |  |
| ODS OUTPUT PARAMETERESTIMATES=POOLED_ESTIMATES;
PROC MIANALYZE PARMS = ESTIMATES ;
CLASS TRT AGE SEX;
MODELEFFECTS INTERCEPT TRT AGE SEX BASVAL ;
RUN;
ODS OUTPUT PARAMETERESTIMATES=POOLED_DIFFS;
PROC MIANALYZE DATA = GLIMMIX_DIFFS ;
MODELEFFECTS ESTIMATE;
STDERR STDERR.   |  |
| RUN;
DATA POOLED_ODDS_RATIO;
SET POOLED_DIFFS;
ODDSRATIO=EXP(ESTIMATE);
ODDS_95LL=EXP(LCLMEAN);
ODDS_95UL=EXP(UCLMEAN);
RUN;   |  |

15.4.2 Change from baseline in the global SANDE score at week 12

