- The remaining missing values in the vehicle group with a monotone missing data pattern will be imputed based on observed data of the control patients with available endpoint, while the remaining missing values in the treatment group with a monotone missing data pattern will be imputed based on observed and imputed data of the control patients;
- All imputed data will be pooled and analyzed, and results will be combined using Rubin's to draw inference.

Whether for MI-RD or wash-out approach, the adjusted estimated treatment difference between cenegermin and vehicle (difference in proportions for Schirmer's test and differences in means for SANDE) will be displayed together with the corresponding two-side 95% confidence interval and p-value.

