# 7.3 Primary estimand

The primary endpoints will be analyzed using treatment policy estimands, defined by the following:

Primary endpoint:

- Population: Adult patients with severe Sjogren's dry eye disease under treatment with Cyclosporine A, as defined by the inclusion-exclusion criteria of the study (and matching the FAS definition);
- Variable: Schirmer I test at week 4;
- Intercurrent event: The occurrence of an intercurrent event is irrelevant. All observed values will be used regardless of occurrence of an intercurrent event. Retrieved drop-outs will be used for data imputation of missing data;
- Population-level summary: Difference in proportion of patients reaching a value of Schirmer I test (without anesthesia) >10mm/5min at week 4.

Coprimary endpoint:

- Population: Adult patients with severe Sjogren's dry eye disease under treatment with Cyclosporine A, as defined by the inclusion-exclusion criteria of the study (and matching the FAS definition);
- Variable: SANDE global score at week 12;

- Intercurrent event: The occurrence of an intercurrent event is irrelevant. All observed values will be used regardless of occurrence of an intercurrent event. Retrieved drop-outs will be used for data imputation of missing data;
- Population-level summary: Difference in means of change from baseline in the global SANDE score at week 12.

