10.1.2 Analysis details

Both co-primary endpoints will be analysed by means of MI-RD to handle missing data. Retrieved drop-out patients are defined as patients who discontinue study treatment and decide to remain in the study by following the schedule of assessments and continuing to adhere to protocol requirements. Consequently, for each primary endpoint, MI will be performed based on the subjects' allocated treatment arm and observed values (baseline and intermediate) as covariates in a regression model using data from Retrieved drop-out patients that have the primary endpoint assessment done.

# 10.1.2.1 Schirmer I test >10mm/5min at week 4

This primary endpoint will be analyzed by means of a logistic regression model adjusting by predefined baseline factors (gender, age class, baseline Schirmer I test value as fixed effects and site as random effect) and a one-sided test will be used to test for differences between treatment groups.

For the imputation of missing data of Schirmer I test, a regression model will be created by including the baseline Schirmer I test value, gender, age class, and Schirmer I test at week 2. Two hundred data sets will be generated, and the random seed number will be 180404. MI will be implemented in the following steps:

1. Partial imputation assuming Missing at Random (MAR) will be carried out to impute intermittent (non-monotone) missing data of Schirmer I test up to week 4 based on a

multivariate joint Gaussian imputation model using the Markov chain Monte Carlo (MCMC) method. A separate imputation model will be used for each treatment arm. In case of non-convergence or non-estimability issues, a single imputation model will be considered (with treatment arm added as explanatory variable to the model). A total of 200 datasets will be created. These datasets will be utilized in Step #2.

- 2. The remaining monotone missing data will be imputed using a MI regression including the same explanatory variables of the previous step. According to MI-RD approach, only non-missing values from retrieve dropouts will be used to inform the regression model.
- 3. Each of the 200 imputed datasets will be analyzed using observed and imputed data. Rubin's rule will be used for combining results to draw inference.

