If there are not enough retrieved dropouts for convergence of MI-RD regression model, a referencebased Multiple Imputation (MI) approach will be adopted to consider a missing not at random (MNAR) mechanism for missing data: imputation of values in the rhNGF arm (above step #2) will be done using the non-missing values from the control group (this approach will be referred as "Copy Reference"). This approach does not assume benefits for rhNGF in case of discontinuation and limits a post-discontinuation clinical effect to that of vehicle. The final decision on the use of the MI-RD vs Copy-Reference for this endpoint will be done at the time of the analysis and reported in the CSR.

Whether for MI-RD or Copy-Reference approach, the adjusted estimated treatment differences in proportions between cenegermin and vehicle at week 4 will be displayed together with the corresponding two-side 95% confidence intervals and p-value.

### 10.1.2.2 Change from baseline in the global SANDE score at week 12

This co-primary endpoint will be analyzed by means of an Analysis of Covariance (ANCOVA) adjusting by pre-defined baseline factors (gender, age class, baseline global SANDE score as fixed effects and site as random effect) and a one-sided test will be used to test for differences between treatment groups. Rules for derivation of SANDE scores are reported in section 12.2.

For the imputation of missing data, a regression model will be created by including the baseline global SANDE score, gender, age class, and intermediate global SANDE scores up to week 12. Two hundred data sets will be generated, and the random seed number will be 252404. MI will be implemented in the following steps:

- 1. Partial imputation assuming MAR will be carried out to impute intermittent (non-monotone) missing data of global SANDE score based on a multivariate joint Gaussian imputation model using the MCMC method. A separate imputation model will be used for each treatment arm. In case of non-convergence or non-estimability issues, a single imputation model will be considered (with treatment arm added as explanatory variable to the model). A total of 200 datasets will be created. These datasets will be utilized in Step #2.
- 2. The remaining monotone missing data will be imputed using a MI regression including the same explanatory variables of the previous step. According to MI-RD approach, only non-missing values from retrieve dropouts will be used to inform the regression model.

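### The Schirmer co-primary estimand is a difference in proportions, but the SAP's primary-analysis code ends in a conditional odds ratio and no method is given for the difference or its confidence interval

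*SAP*

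**What the plan says.** SAP 7.3 gives the population-level summary for this endpoint as "Difference in proportion of patients reaching a value of Schirmer I test (without anesthesia) >10mm/5min at week 4". Protocol 9.4.2 defines it the same way.

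The promised output is on the same scale. SAP 10.1.2.1 says that "the adjusted estimated treatment differences in proportions between cenegermin and vehicle at week 4 will be displayed", with a two-sided 95% CI and a p-value. Protocol 9.4.3.1 makes the same commitment ("difference in proportions for Schirmer's test and differences in means for SANDE) will be displayed together with the corresponding two-side 95% confidence interval"). SAP 10.1.3 and Protocol 9.4.3.2 repeat it for the missing-at-random sensitivity analysis.

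The model is a logistic regression with "gender, age class, baseline Schirmer I test value as fixed effects and site as random effect" (SAP 10.1.2.1). In SAP 15.4.1 it is coded with "DIST=BINARY LINK=LOGIT OR" and a random intercept for site. The last data step computes "ODDSRATIO=EXP(ESTIMATE") and exponentiates the two confidence limits in the same way.

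SAP 10.2.2.1 sends the first key secondary endpoint, Schirmer response at week 8, back to the method of 10.1.2.1.

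**The concern.** The code carries the analysis through to a final pooled result, and that result is not the quantity that the estimand names. A conditional odds ratio and a population difference in proportions are different effect measures, and the first cannot be turned into the second without knowing the risk under vehicle.

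At stake is the reported size of effect, with its interval, for one of two co-primary endpoints. Someone must still produce the promised difference, and several routes are open: crude proportions from the imputed data, subtraction of back-transformed model means, or standardisation over the trial population. These can give different estimates and different intervals. SAP 6.2 places the analyses after lock and unblinding, so a choice not written down now could be made with the allocation known.

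**Working it through.** **1. What the code keeps.** Reading SAP 15.4.1 from the model step onward:

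- Two output tables are saved from the logistic fit: the treatment differences and the parameter estimates. Both are on the logit scale.
- The least-squares means are requested with back-transformation to probabilities (ILINK), but that table is neither saved nor pooled.
- Both saved tables are pooled by Rubin's rules. The pooled treatment difference and its limits are then exponentiated to an odds ratio.
- No step forms a difference of two probabilities, a standard error for it, or an interval.

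**2. The plan's own figure.** SAP section 5 gives a vehicle rate of 33%, a difference of 42 points (hence 75% on cenegermin), 72 evaluable patients at 1:1 (36 per arm), and one-sided alpha 0.025. For a pooled-variance z test of two proportions:

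- mean rate = (0.33 + 0.75)/2 = 0.54
- SE under H0 = √(2 × 0.54 × 0.46/36) = 0.1175
- SE under H1 = √(0.33 × 0.67/36 + 0.75 × 0.25/36) = 0.1065
- z = (0.42 − 1.96 × 0.1175)/0.1065 = 1.78, so power = 96.26%

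The SAP states 96.3%. The trial was therefore sized on an unadjusted difference in proportions, and 33% and 75% act as population responder rates.

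**3. The planned effect on both scales.**

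- Difference: 0.42, with unadjusted 95% CI 0.42 ± 1.96 × 0.1065 = 0.21 to 0.63.
- Odds ratio: (0.75/0.25)/(0.33/0.67) = 6.09, with unadjusted 95% CI about 2.18 to 16.99.

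**4. The odds ratio does not fix the difference.** For vehicle rate c, the cenegermin odds are 6.09 × c/(1 − c), the cenegermin rate is odds/(1 + odds), and the difference is that rate minus c. Only c = 33% comes from the SAP; the other rates are assumed.

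| Vehicle rate | Cenegermin rate | Difference |
|---|---|---|
| 10% | 40.4% | 30 points |
| 20% | 60.4% | 40 points |
| 33% | 75.0% | 42 points |
| 50% | 85.9% | 36 points |

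**5. Subtracting the back-transformed means does not recover the estimand in general.** Those means are taken at average covariates and zero site effect. Because the logit link is non-linear, the risk for an average patient is not the average risk.

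To gauge the size, hold the population rates at 33% and 75%, so the true difference is 42 points. Let site and covariates together spread the linear predictor normally with standard deviation s. Solve for the intercepts a0 and a1 at which expit(a + s × z), averaged over a standard normal z, equals 0.33 and 0.75. Then compute expit(a1) − expit(a0). The documents give no value for s, so every row is an assumption.

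| Assumed s | Difference read from subtracted means | Excess over 42 |
|---|---|---|
| 0.25 | about 42.5 points | 0.5 |
| 0.5 | about 44 points | 2 |
| 1.0 | about 49 points | 7 |
| 1.5 | about 55 points | 13 |

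For comparison, the half-width of the unadjusted 95% CI in step 3 is about 21 points.

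**The case against.** **The text already promises the difference.** This stands in part. A reader might infer from the code that the difference will never be produced, or that the result will be reported on the wrong scale. The documents do not support that: SAP 10.1.2.1 commits to displaying the difference, and only the title of Table 14.2.1.1 is given, so its content cannot be known. What remains is that code headed as the primary analysis omits the promised estimate and that its method is stated nowhere.

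**The test is sound.** This stands in full. A reader might infer that the co-primary test is invalid or that power is lost. With no treatment effect the odds ratio is 1 and the difference is 0, so the logit-scale p-value can serve H01. The sample size reproduces as stated.

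**The numerical error may be negligible.** This also stands as a caution. The model's only random effect is a site intercept, with about 10 sites planned (Protocol 3.2), and eligibility confines baseline Schirmer to 2 to 5 mm (Protocol 4.1), although that alone does not bound its effect. The two larger SDs have no support in the documents, and nothing says that the model means will be subtracted.

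A reader might also treat 75% and 33% as conditional rates and infer that the population difference shrinks to 40, 36 or 31 points at SDs of 0.5, 1.0 and 1.5. SAP section 5 gives them as responder rates and its power reproduces on that footing, so that reading is not supported.

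**Conclusion.** The concern holds as a mismatch between text and code, with an unspecified estimation method. Run as written, the code in SAP 15.4.1 does not yield the declared Schirmer estimand or its interval, and neither document says how to obtain them. That much follows from the documents without any assumption.

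The numerical consequence is uncertain. One odds ratio of 6.09 spans 30 to 42 points over the vehicle rates tried. The shortcut of subtracting model means would overstate a true 42 points by roughly half a point to 13 points, depending on a spread that the documents do not give; the lower end would matter little beside the sampling error. The matter concerns estimation and reporting, and should be settled before unblinding.

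**What to change.** Add a standardisation step to SAP 10.1.2.1 and to the code in 15.4.1. In each of the 200 imputed datasets:

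1. Fit the logistic model as now specified.
2. Predict every FAS patient's probability of response twice, once under cenegermin and once under vehicle, with the patient's own covariates. Integrate the site random intercept over its estimated distribution; setting it to zero would bring back part of the discrepancy in step 5 of the working.
3. Average the predictions under each treatment, take the difference, and obtain its standard error by the delta method or the bootstrap. Name which one in the SAP.

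Pool the 200 differences and standard errors by Rubin's rules, and report the pooled risk difference with its 95% CI as the primary estimate. Keep the logit-scale p-value for the test of H01 and the odds ratio as supportive. Apply the same step to the missing-at-random sensitivity analysis (SAP 10.1.3) and to the week 8 Schirmer key secondary endpoint (SAP 10.2.2.1).

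The cost is some additional code, including the integration over site, and a short paragraph in the SAP. No new data are needed, and the test, sample size and power do not change.
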